2.5.2.3 Handling of intercurrent events

See [Section 2.5.2.1](#)

2.5.2.4 Handling of missing values

See [Section 2.5.1.4](#) for missing data of continuous variables. Missing data of response variables will be derived using the multiply imputed data for corresponding continuous variables.

2.5.2.5 Sensitivity analyses

Not applicable

2.5.2.6 Supplementary analyses

For binary variables (UAS7 \leq 6 at Week 12, UAS7 = 0 at Week 12, UAS7 \leq 6 at Week 2, DLQI 0/1 at Week 12), the treatment difference adjusting covariates as region, prior exposure to anti-IgE biologics and baseline UAS7 score will be provided.

2.6 Analysis plan for the scenario with ISS7 and HSS7 as the co-primary efficacy endpoints

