The proportion of participants with $UAS7 \leq 6$ at Week 2 will be analyzed using a logistic regression model including treatment group, region, prior exposure to anti-IgE biologics and baseline UAS7 score as covariate.

6. DLQI = 0/1 at Week 12

The proportion of participants with overall DLQI scores ≤ 1 at Week 12 will be analyzed using a logistic regression model which includes treatment group, region, prior exposure to anti-IgE biologics and baseline DLQI score.

7. Cumulative number of weeks with an $UAS7 \leq 6$ response between baseline and Week 12

The cumulative number of weeks achieving $UAS7 \leq 6$ response between baseline and Week 12 will be modelled using a negative binomial regression model with log link, using treatment group, region, and prior exposure to anti-IgE biologics. The patient's time in the treatment period up to Week 12 (natural log of proportion of time in treatment period, i.e., natural log of [number of weeks with the response variable in treatment period/12 weeks]) is used as an offset variable to obtain the $UAS7 \leq 6$ rate, adjusted for the varying lengths of patient's time in the randomized treatment period.

8. Cumulative number of weeks with an $AAS7 = 0$ response between baseline and Week 12

The cumulative number of weeks achieving $AAS7 = 0$ response between baseline and Week 12 will be modelled using a negative binomial regression model with log link, using treatment

group, region, prior exposure to anti-IgE biologics and baseline AAS7 = 0 status. The patient's time in the treatment period up to Week 12 (natural log of proportion of time in treatment period, i.e., natural log of [number of weeks with the response variable in treatment period/12 weeks]) is used as an offset variable to obtain the AAS7=0 rate, adjusted for the varying lengths of patient's time in the randomized treatment period.

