5.4.2 Analysis supporting secondary objective(s)

5.4.2.1 Logistic regression

Binary outcome variables including UAS7=0 “Complete Response” or UAS7 \leq 6 “Disease control” will be evaluated using a logistic regression model with treatment, and actual randomization strata variables (i.e. geographic region and prior exposure to anti-IgE biologics). Odds ratios will be computed for treated participants with response relative to control participants utilizing the logistic regression model fitted.

The odds ratio will be calculated such that an odds ratio > 1 is favorable for LOU064 drug. The SAS procedure PROC LOGISTIC will be used for this analysis with the following code:

```
proc logistic data = ...;
by_imputation_;
class trt01p antige region/ param = glm;
model response (event = '1') = trt01p antige region baseline;
estimate "LOU064 vs Placebo" trt01p 1 -1;
```

```
ods output ESTIMATEs=estimates;  
run;
```

If separation occurs, the Firth's method will be implemented using the firth option in the MODEL statement.

The SAS procedure PROC MIANALYZE will be used to combine the results. The odds ratios and the 95% confidence interval for the odds ratio will be generated using an exponential transformation of the model estimates.

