5.4.2.2 Covariate adjustment for treatment difference with binary outcome variable

For binary outcome variables, the treatment difference and the corresponding 95 % confidence interval will be provided besides odds ratios.

FDA guidance introduces the following steps for one statistically reliable method of covariate adjustment for treatment difference with binary outcome ([Adjusting for Covariates in Randomized Clinical Trials for Drugs and Biological Products, Guidance for Industry, Draft guidance, May 2021](#)).

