5.4.3 Multiple imputations

Multiple imputation is a simulation-based approach where missing values are replaced by multiple Bayesian draws from the conditional distribution of missing data given the observed data and covariates, creating multiple completed data sets. These completed data sets can then be analyzed using standard methods. [Rubin \(1987\)](#) presented rules how to combine the multiple sets of estimates to produce overall estimates and confidence intervals that adequately incorporate missing data uncertainty. The multiple imputation analysis will be imputed based on the individual treatment arm information.

Missing values for UAS7/HSS7/ISS7/AAS7/DLQI will be imputed separately. The imputation is done on the original post-baseline score and the imputation model will include treatment group, the corresponding baseline score, actual randomization strata variables, week and both interaction of treatment by week and interaction of the corresponding baseline score by week. The number of imputations is 100. The imputed values may exceed possible range of variables. In this case, the imputed values which exceed possible maximum value (e.g., 42 for UAS7) will be replaced with the maximum value, the imputed values which exceed possible minimum value (e.g., 0 for UAS7) will be replaced with the minimum value.

Multiple imputation will be implemented using the RMConjPlus20 and RefBTBV04 SAS macro. The macros are available from the website of London school of Hygiene & tropical

medicine (LSHTM) on <https://www.lshtm.ac.uk/research/centres-projects-groups/missing-data#dia-missing-data>. The purpose and activities of each of the two macros is described below. For more details of these two macros please see “The RMConjPlus and RefbTbV SAS macros” by James H. Roger (2023) at <https://www.lshtm.ac.uk/research/centres-projects-groups/missing-data#dia-missing-data>.

The %RefBTBV SAS macro is used to set up the design matrix for reference-based imputation. This macro creates an input data set for %RMConjPlus by generating the required Treatment*Visit part of the design matrix based on the chosen reference-based imputation method (J2R, CIR, CR, etc.).

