The %RMConjPlus SAS macro is applied for reference-based imputation (J2R in this study) where an individual patient’s means model for those on active treatment is modified after trial withdrawal to closer represent the reference (placebo) arm (Carpenter, 2013). The imputation is done by two stages. In stage 1, it fits a Bayesian Repeated Measures model where there are a fixed number of visits. A multivariate Normal model is assumed with a series of one or more unstructured covariance matrices. Each subject uses only one of these matrices. Data within subject are related while data between subjects are assumed independent. In stage 2, it builds a set of imputed values for missed observations directly as part of the MCMC process using an pre-specified imputation model (J2R in this study).

This is example code to implement the primary analysis:

```
%RefbTBV(  
Data= inputdata,  
Out=RefB_Out,  
Subject= usubjid,  
Visit= week,  
OnTreatment= OT,  
Treatment= group,  
Method= Mymethod,  
Reference= Placebo);
```

where usubjid = unique subject identifier

week =study week
group= planned treatment group
(1 = LOU064 2 = Placebo)
OT = indicator of on/off treatment status

Mymethod = Method used to impute missing data. For example, this could be specified as J2R to indicate that Jump to reference is used to impute missing data for LOU064 patients who discontinued treatment and MAR otherwise, where Placebo is used as reference.

```
%RMConjPlus (  
Data=RefB_Out ,  
OUT_Imp= out_imp,  
Subject=usubjid,  
Visit=week,  
Response=aval,  
Model=&RefbTbV base*week antige region,  
Class=week group antige region,
```

```
seed=23012,  
Nimpute=100  
) ;
```

Where usubjid = unique subject identifier
week = study week
aval = UAS7 weekly score
base = baseline UAS7 score
antige = prior exposure to anti-IgE biologics
region = geographic region
&RefbTbV = design matrix generated from RefbTBV macro.

If the imputation model has warnings regarding auto-correlation, a larger number of autocorlag parameter could be specified (e.g., autocorlag=70 in the RMConjPlus macro). Any missing baseline values will be multiply imputed using baseline characteristics variables before putting into the %RefBTBV and %RMConjPlus using Proc MI. The example code for imputing baseline of DLQI is shown below:

```
proc mi data= dlqi_base_imp out=dlqi_regpmm nimpute = 100 seed = 23012;  
class group sex antige region;  
FCS regpmm(base/details);  
var age sex group antige region base ;  
run;
```

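### The supplementary risk difference for DLQI 0/1 is adjusted for baseline UAS7, while the logistic model and the imputation model for the same endpoint use baseline DLQI

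*SAP*

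**What the plan says.** SAP 2.5.2.6 covers four binary endpoints in one sentence: UAS7 ≤ 6 at Week 12, UAS7 = 0 at Week 12, UAS7 ≤ 6 at Week 2 and DLQI 0/1 at Week 12. The list ends with DLQI and runs straight into the covariates: "DLQI 0/1 at Week 12), the treatment difference adjusting covariates as region". For all of them the plan is that "the treatment difference adjusting covariates as region, prior exposure to anti-IgE biologics and baseline UAS7 score will be provided". The only baseline score named for all four is UAS7.

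For the tested analysis of DLQI 0/1, SAP 2.5.2.2 item 6 specifies a "logistic regression model which includes treatment group, region, prior exposure to anti-IgE biologics and baseline DLQI score". Protocol 12.5.1 lists the same covariates.

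Three other places bear on the point:

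- SAP 5.4.2.2 says that for binary outcomes "the treatment difference and the corresponding 95 % confidence interval will be provided besides odds ratios". Its visible text lists no covariates.
- SAP 5.4.2.1 gives the logistic code with a generic term, "model response (event = '1') = trt01p antige region baseline", and does not define that term for each endpoint.
- SAP 5.4.3 imputes each score separately and says "the imputation model will include treatment group, the corresponding baseline score, actual randomization strata variables".

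SAP 2.6.2.6 refers back to 2.5.2.6, so the co-primary scenario inherits the same text.

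**The concern.** The odds ratio and the risk difference for DLQI 0/1 are meant to be read side by side, yet as written they condition on different baselines. The risk difference leaves out the baseline of its own outcome, and no reason is given.

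It looks like a drafting slip. Baseline UAS7 is the natural covariate for the other three endpoints in the sentence and fails to match only for DLQI. Elsewhere, wherever an efficacy model includes a baseline score, it is the endpoint's own: UAS7, ISS7 or HSS7 in the MMRMs, AAS7 = 0 status in the AAS7 count model, and DLQI in the DLQI logistic model.

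What is at stake is modest. A programmer who follows 2.5.2.6 literally would use baseline UAS7, and one who reuses the logistic model would use baseline DLQI, so the plan does not settle which result is reported. The interval may also be slightly wider than it need be. In addition, the risk difference would adjust for a score that is absent from the model used to impute DLQI, and omit the one that is present. This last effect concerns imputed values only and is probably small.

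**Working it through.** **Text comparison for DLQI 0/1 at Week 12**

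| Analysis | Place | Baseline score used |
|---|---|---|
| Logistic odds ratio | SAP 2.5.2.2 item 6; protocol 12.5.1 | DLQI |
| Imputation of missing scores | SAP 5.4.3 | DLQI (the corresponding score) |
| Adjusted treatment difference | SAP 2.5.2.6; by reference 2.6.2.6 | UAS7 |

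Baseline DLQI is available. It is scheduled at baseline (protocol Table 8-1, SAP Table 2-6), and missing values are multiply imputed; SAP 5.4.3 uses this very case as its illustration ("The example code for imputing baseline of DLQI is shown below").

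**Size of the precision effect.** The plan gives no DLQI 0/1 rate, power or precision figure, so there is nothing of its own to reproduce. It also gives no prognostic strength for either baseline. Everything below rests on assumptions.

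Assume that baseline UAS7 explains 2-5% of the outcome variance and baseline DLQI 5-10%. The variance of the adjusted difference is then roughly proportional to 1 − R², and the ratio (DLQI-adjusted over UAS7-adjusted) is (1 − R²_DLQI)/(1 − R²_UAS7):

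| R² UAS7 | R² DLQI | Variance ratio | CI width ratio (square root) |
|---|---|---|---|
| 2% | 5% | 0.95/0.98 = 0.97 | 0.98 |
| 2% | 10% | 0.90/0.98 = 0.92 | 0.96 |
| 5% | 5% | 0.95/0.95 = 1.00 | 1.00 |
| 5% | 10% | 0.90/0.95 = 0.95 | 0.97 |

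So the variance is 0-8% lower with baseline DLQI, and the interval at most about 4% shorter.

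In absolute terms, take assumed response rates of 0.35 and 0.15 with 300 and 150 participants. The unadjusted SE is √(0.35×0.65/300 + 0.15×0.85/150) = 0.0401, and the 95% half-width is 1.96 × 0.0401 = 0.0786. In the most favourable corner the half-width is 0.0786 × √0.98 = 0.0778 with baseline UAS7 and 0.0786 × √0.90 = 0.0746 with baseline DLQI. The gain is about 0.3 of a percentage point.

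**Simulation.** For each setting, 3,000 trials of 300:150 were generated. A logistic model with treatment and one baseline was fitted, and the risk difference was obtained by averaging predicted risks under each arm. Region and prior anti-IgE exposure were left out. Assumed rates were 0.35 vs 0.15 and 0.45 vs 0.25.

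| Log-odds per SD (DLQI; UAS7) | Correlation of baselines | SE ratio, UAS7-adjusted / DLQI-adjusted |
|---|---|---|
| −1.0; 0 | 0.3 to 0.7 | 1.031 to 1.080 |
| −0.5; 0 | 0.3 to 0.7 | 1.007 to 1.023 |
| −0.5; −0.3 | 0.5 | 1.011 to 1.017 |
| −0.3; −0.3 | 0.5 | 0.996 to 1.000 |
| 0; −0.5 | 0.5 | 0.984 to 0.985 |

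The mean estimate lay between 0.197 and 0.202 for a true difference of 0.20. The two adjusted means never differed by more than 0.0003.

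The extreme ratio of 1.080 would mean an interval 1 − 1/1.080 = 7% shorter. It arises where baseline DLQI removes 1 − (0.0409/0.0444)² = 15% of the unadjusted variance, which is above the 10% ceiling assumed in the R² calculation, so the two results agree.

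**The case against.** The best defence is that one prespecified disease-activity covariate for all supplementary differences is a valid choice. Randomisation means that the adjusted difference targets the same quantity with either baseline. The tested DLQI result already uses baseline DLQI. All of that stands, and it limits the point to one of consistency.

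A reader might infer that the risk difference certainly loses precision. The documents do not support this. They give no R², no correlation between the two baselines and no DLQI 0/1 rates. The gain is nil where both are equally prognostic and slightly reversed where only baseline UAS7 is.

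A reader might also infer that matching the covariates would make the two effect measures interchangeable. It would not: the odds ratio is conditional on the covariates, and the risk difference is on another scale. Matching aligns the working models and no more.

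Finally, SAP 5.4.2.2 announces steps for the covariate adjustment that do not appear in the available text. They may name covariates by endpoint. If they do, 2.5.2.6 would still need to agree with them, because its wording is explicit.

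**Conclusion.** The mismatch is real, unexplained and present in both scenarios. It is a minor consistency defect. It does not mean that the DLQI 0/1 risk difference is biased or that the DLQI hypothesis test is compromised: the difference is supplementary, lies outside the testing hierarchy, and shows no shift with either baseline.

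The possible cost is some precision. Under the assumed R² ranges (2-5% for UAS7, 5-10% for DLQI), the variance would be 0-8% lower with baseline DLQI and the interval at most about 4% shorter. If only baseline UAS7 predicts the outcome, UAS7 adjustment is better by roughly 2% of the SE. The text mismatch is certain; the precision effect is conditional on inputs that the documents do not supply. The case for alignment holds even if the precision gain is zero.

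**What to change.** In SAP 2.5.2.6, keep region and prior anti-IgE exposure, and replace the single named baseline with the score that corresponds to each endpoint: baseline UAS7 for the three UAS7 endpoints and baseline DLQI for DLQI 0/1 at Week 12. Section 2.6.2.6 then follows by reference. It would help to define the generic baseline term in 5.4.2.1 for each endpoint as well. If baseline UAS7 was intended for DLQI 0/1, one sentence giving the reason would do instead.

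The cost is a few words and one variable in the code, with no new data. Timing needs care. SAP amendments 2 to 4 are marked as before the primary analysis, and amendment 5 as before the final analysis, so the primary analysis may already have been run; the documents do not say. If it has, label the change as made after it and name the covariate in the table footnote.

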2.6.1 Analysis supporting primary objective(s)

All analyses for efficacy data will be based on the FAS.

2.6.1.1 Primary endpoints

Primary estimand for scenario with ISS7 and HSS7 as the co-primary efficacy endpoints

The primary clinical question of interest is: What is the effect of remibrutinib treatment versus placebo on the change from baseline in ISS7 score and change from baseline in HSS7 score at Week 12 after treatment in adult participants with CSU who are inadequately controlled by H1-antihistamine and receiving a stable locally label approved dose of a second generation H1-antihistamine, regardless of treatment discontinuation for any reason and regardless of intake of a different second generation H1-antihistamine as rescue medication and considering strongly confounding prohibited medication as an unfavorable outcome?

The co-primary efficacy endpoints are the absolute change from baseline in **ISS7 score at Week 12** and absolute change from baseline in **HSS7 score at Week 12**, which is the ISS7 score (respectively HSS7 score) at Week 12 minus the ISS7 score (respectively HSS7 score at baseline). The weekly scores ISS7 and HSS7 range from 0-21, and will be derived by adding up the average daily scores of the 7 days preceding the visit.

Derivation of primary endpoints

See [Section 2.5.1.1](#)

2.6.1.2 Statistical hypothesis, model, and method of analysis

The statistical hypothesis test for the co-primary endpoints tests the union null hypothesis that the absolute change from baseline in ISS7 score at Week 12 in remibrutinib is not superior to the placebo group or the absolute change from baseline in HSS7 score at Week 12 in remibrutinib is not superior to the placebo group i.e.:

$H_{01a}: \mu_{\text{remibrutinib}} \geq \mu_{\text{Placebo}}$ versus $H_{A1a}: \mu_{\text{remibrutinib}} < \mu_{\text{Placebo}}$

where μ is the mean change from baseline in ISS7 at Week 12.

$H_{01b}: \mu_{\text{remibrutinib}} \geq \mu_{\text{Placebo}}$ versus $H_{A1b}: \mu_{\text{remibrutinib}} < \mu_{\text{Placebo}}$

where μ is the mean change from baseline in HSS7 at Week 12.

The union null hypothesis is rejected if both elementary null hypotheses (H_{01a} , H_{01b}) are rejected.

A linear mixed model with repeated measures (MMRM) will be used to estimate treatment differences for change from baseline in ISS7 score (respectively HSS7) at Week 12, based on the FAS. The MMRM model will include treatment group, baseline ISS7 score (respectively HSS7), randomization strata variables, week and both interaction of treatment by week and interaction of baseline ISS7 score (respectively HSS7) by week as fixed effects. Repeated measures within participant are modeled using an unstructured covariance of the error terms. Additional important covariates may be added to the model. For the primary analysis, data up to Week 12 will be used in the model. The treatment difference LOU064 25 mg – placebo at Week 12 will be estimated using the LS mean and 95% CI, and p-value for treatment comparison will be presented.

The detailed testing strategy including the primary endpoint analysis is provided in [Section 2.6.2.2](#).

2.6.1.3 Handling of intercurrent events

See [Section 2.5.2.1](#)

2.6.1.4 Handling of missing values

See [Section 2.5.1.4](#)

2.6.1.5 Sensitivity analyses

The following sensitivity analysis will be performed for the primary estimand to assess the robustness of the estimation in the presence of deviations from the assumptions specified in the primary analysis. The sensitivity analysis will be implemented with the same target population, the primary variables and the summary measure as for the primary estimand but using the different assumptions or handling of intercurrent events.

Sensitivity analysis: The change from baseline in ISS7 and HSS7 score up to Week 12 will be imputed using zero (i.e. no clinical improvement from baseline) for the intercurrent event of “Intake of strongly confounding prohibited medication (e.g. biologics treatment at any time before Week 12, cyclosporin after Week 8 to Week 12, systemic corticosteroids after Week 8 to Week 12)” handled with composite strategy.

2.6.1.6 Supplementary analyses

Supplementary estimand

The clinical question of interest is: What is the effect of remibrutinib treatment versus placebo on the change from baseline in ISS7 score and change from baseline in HSS7 score at Week 12 after treatment in adult participants with CSU who are inadequately controlled by H1-antihistamine and receiving a stable locally label approved dose of a second generation H1-antihistamine, regardless of treatment discontinuation for any reason and regardless of intake of a different second generation H1-antihistamine as rescue medication, and as if strongly confounding prohibited medication was not taken?

The supplementary estimand is described by the following attributes:

1. **Population:** patients with inadequately controlled CSU despite treatment with second generation H1-antihistamine who have CSU duration ≥ 6 months, a UAS7 score ≥ 16 , ISS7 score ≥ 6 and HSS7 score ≥ 6 in the last 7 days prior to randomization.
2. **Endpoint:** Change in ISS7 from baseline at Week 12 and change in HSS7 from baseline at Week 12.
3. **Treatment of interest:** the randomized study treatment (remibrutinib 25 mg b.i.d. or placebo) regardless of treatment compliance, with background medication of local approved second generation H1-antihistamine, and a different second generation H1-antihistamine as rescue medication.
4. **Summary Measurement:** the mean difference between treatment groups.
5. **Handling of intercurrent events:**
 - Discontinuation of study treatment due to any reason, treatment non-compliance (dose interruption): **Treatment policy strategy** (same as in [Section 2.5.1.3](#))
 - Intake of rescue medication, switch of background medication, intake of other prohibited medication, or participants non-compliant to treatment prior to Week 12: **Treatment policy strategy** (same as in [Section 2.5.1.3](#))
 - Intake of strongly confounding prohibited medication (e.g. biologics treatment at any time before Week 12, cyclosporin after Week 8 to Week 12, systemic corticosteroids after Week 8 to Week 12): **Hypothetical strategy** (irrespective of potential occurrence of other intercurrent events) (same as in [Section 2.5.1.6](#))

For detailed data handling, please see [Section 2.5.1.3](#) and [Section 2.5.1.4](#).

